7.2.4.1 Additional biomarker assessments

[REDACTED]

[REDACTED]

[REDACTED]

[REDACTED]

[REDACTED]

[REDACTED]

[REDACTED]

[REDACTED]

7.2.6 Patient reported outcomes

Two questionnaires will be used in this study to capture PROs: Functional Assessment of Cancer Therapy-Leukemia (FACT-Leu) and EQ-5D-5L. Brief description of each questionnaire is given in the sections below.

The patient should be given the questionnaire(s) to be completed at the scheduled visit before other clinical assessments are conducted. Questionnaires should be completed in the language the respondent is most familiar with, at the scheduled visit before the patient sees the investigator for clinical assessments. The patient should be given sufficient space and time to complete the questionnaire.

[REDACTED]

Reason for missing data at scheduled visit will also be captured ('patient refused due to poor health', 'patient refused (unrelated to health)', 'study staff felt patient was too ill', 'patient missed appointment', 'other reasons').

Data from both questionnaires will be captured electronically using dedicated devices. Instructions for operating the devices will be available to each study site. In addition detailed instructions relating to the administrative procedures of the questionnaires will be provided to the sites in a separate document. Patient's refusal to complete all or any part of a questionnaire should be documented in the study data capture system.

FACT-Leu

The FACT-Leu is a questionnaire to assess the quality of life in patients with leukemia. It consists of a general quality of life instrument (FACT-G) and a condition specific module Leu. The FACT-Leu is a fully validated QOL questionnaire applicable for patients with leukemia and includes a module which assesses specific concerns of patients with leukemia. The FACT-G has 27 statements that patients will need to endorse on a five-point scale (not at all, a little, somewhat, quite a bit, very much). The statements cover five subscales (Physical Well-Being, Social/Family Well-Being, Emotional Well-Being, Functional Well-Being and Additional Concerns). The Leu module consists of 17 statements patients need to endorse on an identical five-point scale. The recall period is "Past 7 days", and the questionnaire requires approximately 5 minutes to complete.

EQ-5D-5L

The EQ-5D is a widely used, self-administered questionnaire designed to assess health status in adults. The EQ-5D-5L essentially consists of 2 pages: the EQ-5D descriptive system and the EQ visual analogue scale (EQ VAS). The descriptive system comprises five dimensions: mobility, self-care, usual activities, pain/discomfort and anxiety/depression. Each dimension has 5 levels: no problems, slight problems, moderate problems, severe problems and extreme problems.

[figure not shown]
Patients rate each of these items: no problems, slight problems, moderate problems, severe problems and extreme problems. A composite health index is then defined by combining the levels for each dimension. The second section of the questionnaire measures self-rated (global) health status utilizing a vertically oriented visual analogue scale where 100 represents the "best possible health state" and 0 represents the "worst possible health state." Respondents are asked to rate their current health by placing a mark along this continuum. The recall period is "today," and the questionnaire requires approximately 5 minutes to complete.

8 Safety monitoring and reporting

8.1 Adverse events

8.1.1 Definitions and reporting

An adverse event is defined as the appearance of (or worsening of any pre-existing) undesirable sign(s), symptom(s), or medical condition(s) that occur after patient's signed informed consent has been obtained.

Abnormal laboratory values or test results occurring after informed consent constitute adverse events only if they induce clinical signs or symptoms, are considered clinically significant, require therapy (e.g., hematologic abnormality that requires transfusion or hematological stem cell support), or require changes in study medication(s).

Adverse events that begin or worsen after informed consent should be recorded in the Adverse Events CRF. Conditions that were already present at the time of informed consent should be recorded in the Medical History CRF. Adverse event monitoring should be continued for at least 30 days following the last dose of study treatment. Adverse events (including lab abnormalities that constitute AEs) should be described using a diagnosis whenever possible, rather than individual underlying signs and symptoms. When a clear diagnosis cannot be identified, each sign or symptom should be reported as a separate Adverse Event.

Adverse events will be assessed and graded according to the CTCAE version 5.0.

If CTCAE grading does not exist for an adverse event, the severity of mild, moderate, severe, and life-threatening, death related to the AE corresponding respectively to Grades 1 - 5, will be used. Information about any deaths (related to an Adverse Event or not) will also be collected through a Death form.

The occurrence of adverse events should be sought by non-directive questioning of the patient during the screening process after signing informed consent and at each visit during the study. Adverse events also may be detected when they are volunteered by the patient during the screening process or between visits, or through physical examination, laboratory test, or other assessments. As far as possible, each adverse event should be evaluated to determine:

1. The severity grade (CTCAE Grade 1-5)
2. Its duration (start and end dates)
3. Its relationship to the study treatment (related, not related)
4. Action taken with respect to study treatment (dose increased, dose not changed, dose reduced, drug interrupted, drug withdrawn, unknown, not applicable)
5. Whether medication or therapy was given (no concomitant medication/non-drug therapy, concomitant medication/non-drug therapy)
6. Whether it is serious, where a SAE is defined as in [Section 8.2.1](#) and which seriousness criteria have been met
7. Outcome (not recovered/not resolved, recovered/resolved, recovered/resolved with sequelae, fatal, unknown)
8. If the event worsens, the event should be reported a second time in the CRF noting the start date when the event worsens in toxicity. For grade 3 and 4 adverse events only, if improvement to a lower grade is determined a new entry for this event should be reported in the CRF noting the start date when the event improved from having been Grade 3 or Grade 4.

All adverse events should be treated appropriately. If a concomitant medication or non-drug therapy is given, this action should be recorded on the Adverse Event CRF.

Once an adverse event is detected, it should be followed until its resolution or until it is judged to be permanent, and assessment should be made at each visit (or more frequently, if

necessary) of any changes in severity, the suspected relationship to the study treatment, the interventions required to treat it, and the outcome.

Treatment failure or relapse (including fatal outcomes), if documented by use of appropriate method should not be reported as a serious adverse event.

Adverse events separate from relapse or treatment failure will be reported as per usual guidelines used for such events with proper attribution regarding relatedness to the drug.

8.1.2 Laboratory test abnormalities

8.1.2.1 Definitions and reporting

Laboratory abnormalities that constitute an AE in their own right (are considered clinically significant, induce clinical signs or symptoms, require concomitant therapy or require changes in study treatment), should be recorded on the AEs CRF. Whenever possible, a diagnosis, rather than a symptom should be provided (e.g. anemia instead of low hemoglobin). Laboratory abnormalities that meet the criteria for Adverse Events should be followed until they have returned to normal or an adequate explanation of the abnormality is found. When an abnormal laboratory or test result corresponds to a sign/symptom of an already reported adverse event, it is not necessary to separately record the lab/test result as an additional event.

Laboratory abnormalities, that do not meet the definition of an adverse event, should not be reported as adverse events. A Grade 3 or 4 Event (severe) as per CTCAE does not automatically indicate a SAE unless it meets the definition of serious as defined below and/or as per investigator's discretion. A dose hold or medication for the lab abnormality may be required by the protocol in which case the lab abnormality would still, by definition, be an adverse event and must be reported as such.

8.1.3 Adverse events of special interest

Adverse events of special interest (AESI) are defined as events (serious or non-serious) which are ones of scientific and medical concern specific to Midostaurin, for which ongoing monitoring and rapid communication by the investigator to the sponsor should be appropriate. Such events may require further investigation in order to characterize and understand them.

AESI are defined on the basis of an ongoing review of the safety data. AESI are discussed in detail in the Investigator Brochure.

8.2 Serious adverse events

8.2.1 Definitions

Serious adverse event (SAE) is defined as one of the following:

- Is fatal or life-threatening
- Results in persistent or significant disability/incapacity
- Constitutes a congenital anomaly/birth defect
- Is medically significant, i.e., defined as an event that jeopardizes the patient or may require medical or surgical intervention to prevent one of the outcomes listed above

- Requires inpatient hospitalization or prolongation of existing hospitalization,
- Note that hospitalizations for the following reasons should not be reported as serious adverse events:
 - Routine treatment or monitoring of the studied indication, not associated with any deterioration in condition
 - Elective or pre-planned treatment for a pre-existing condition that is unrelated to the indication under study and has not worsened since signing the informed consent
 - Social reasons and respite care in the absence of any deterioration in the patient's general condition
- Note that treatment on an emergency outpatient basis that does not result in hospital admission and involves an event not fulfilling any of the definitions of a SAE given above is not a serious adverse event.

8.2.2 Reporting

To ensure patient safety, every SAE, regardless of suspected causality, occurring after the patient has provided informed consent and until at least 30 days after the patient has stopped study treatment must be reported to Novartis within 24 hours of learning of its occurrence.

Any additional information for the SAE including complications, progression of the initial SAE, and recurrent episodes must be reported as follow-up to the original episode within 24 hours of the investigator receiving the follow-up information. An SAE occurring at a different time interval or otherwise considered completely unrelated to a previously reported one should be reported separately as a new event.

Any SAEs experienced after the 30 day safety evaluation follow-up period should only be reported to Novartis if the investigator suspects a causal relationship to the study treatment.

Information about all SAEs is collected and recorded on the Serious Adverse Event Report Form; all applicable sections of the form must be completed in order to provide a clinically thorough report. The investigator must assess and record the relationship of each SAE to each specific study treatment (if there is more than one study treatment), complete the SAE Report Form in English, and submit the completed form within 24 hours to Novartis. Detailed instructions regarding the SAE submission process and requirements for signatures are to be found in the investigator folder provided to each site.

Follow-up information is submitted in the same way as the original SAE Report. Each re-occurrence, complication, or progression of the original event should be reported as a follow-up to that event regardless of when it occurs. The follow-up information should describe whether the event has resolved or continues, if and how it was treated, whether the blind was broken or not, and whether the patient continued or withdrew from study participation.

If the SAE is not previously documented in the Investigator's Brochure or Package Insert (new occurrence) and is thought to be related to the Novartis study treatment, an oncology Novartis Chief Medical Office and Patient Safety (CMO&PS) department associate may urgently require further information from the investigator for Health Authority reporting. Novartis may need to issue an Investigator Notification (IN), to inform all investigators involved in any study with the same drug that this SAE has been reported. Suspected Unexpected Serious Adverse

Reactions (SUSARs) will be collected and reported to the competent authorities and relevant ethics committees in accordance with Directive 2001/20/EC or as per national regulatory requirements in participating countries.

8.3 Emergency unblinding of treatment assignment

Emergency unblinding should only be undertaken when it is essential for effective treatment of the patient. Most often, study treatment discontinuation and knowledge of the possible treatment assignments are sufficient to treat a study patient who presents with an emergency condition. Emergency code breaks are performed using the IRT. When the investigator contacts the IRT to unblind a patient, he/she must provide the requested patient identifying information and confirm the necessity to unblind the patient. The investigator will then receive details of the drug treatment for the specified patient and a fax confirming this information. The system will automatically inform the Novartis monitor for the site and the Study Lead that the code has been broken.

It is the investigator's responsibility to ensure that there is a procedure in place to allow access to the IRT in case of emergency. The investigator will inform the patient how to contact his/her backup in cases of emergency when he/she is unavailable. The protocol number, study treatment name if available, subject number, and instructions for contacting the local Novartis country pharma organization (CPO) (or any entity to which it has delegated responsibility for emergency code breaks) will be provided to the patient in case emergency unblinding is required at a time when the investigator and backup are unavailable. However, if a mechanism is already in place to ensure that the investigator and/or back-up can always be reached in case of emergency then the procedure above is not required.

[figure not shown]
The appropriate personnel from the site and Novartis will assess whether study treatment should be discontinued for any patient whose treatment code has been broken inadvertently for any reason.

8.4 Pregnancies

To ensure patient safety, each pregnancy occurring while the patient is on study treatment must be reported to Novartis within 24 hours of learning of its occurrence. The pregnancy should be followed up to determine outcome, including spontaneous or voluntary termination, details of the birth, and the presence or absence of any birth defects, congenital abnormalities, or maternal and/or newborn complications.

Pregnancy should be recorded on a Clinical Trial Pregnancy Form and reported by the investigator to the oncology Novartis CMO&PS. Pregnancy follow-up should be recorded on the same form and should include an assessment of the possible relationship to the study treatment for any pregnancy outcome. Any SAE experienced during pregnancy must be reported on the SAE Report Form.

Pregnancy outcomes should be collected for the female partners of any males who took study treatment in this study. Consent to report information regarding these pregnancy outcomes should be obtained from the mother.

If pregnancy occurs in a patient in the study, the **study treatment must be discontinued**, though the patient may stay in the study and follow the assessments, if she wishes to do so. All assessments that are considered as a risk during pregnancy must not be performed. The patient may continue all other protocol assessments.

Follow up of the pregnancy (female patient or female partner of patient) should be according to the following schedule:

- Tracking of pregnancy cases occurs until after Expected Delivery Date (EDD) for all prospective pregnancy cases received from clinical studies (including pregnancies where the patient was exposed to placebo or comparator and pregnancies due to the conduct of the study).
- EDD +1 month (mandatory for all cases). Requesting the pregnancy outcome and other clinically relevant pregnancy data or changes in data.
- EDD+2 month (mandatory if no answer is obtained after request at EDD+1 month). A reminder letter for the outcome.
- The follow up at EDD+3 months is mandatory for all cases of live birth. Information on the status of the baby 3 months after delivery and information on any development issue or abnormality that would not be seen at birth must be collected.
- The follow up at EDD+12 months is mandatory for all cases of live birth. Information on the status of the baby 12 months after delivery and information on any development issue or abnormality that would not be seen at birth must be collected.

If the pregnancy case is lost to follow-up (e.g. no response after 3 attempts) this information must be transferred to the Safety Desk of the CPO.

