Based on recombinant enzymes and human liver microsomes, the CYP3A4 is the major enzyme involved in midostaurin oxidative metabolism. Midostaurin, CGP52421 and CGP62221 were found to inhibit the following cytochromes *in-vitro*: CYP1A2, CYP2B6, CYP2C8, CYP2C9, CYP2D6, CYP2E1 and CYP3A4. It also induces the following cytochromes: CYP1A2, CYP2C8, CYP2C9, CYP2B6 and CYP3A4. The results of the net effect model suggest that an impact of midostaurin and/or CGP52421 and CGP62221 is expected on the following CYP: CYP3A4, CYP2C8 and CYP2B6.

In vitro experiments demonstrated as well that midostaurin, CGP52421 and CPG62221 can potentially inhibit P-glycoprotein (P-gp) inhibitor with an IC₅₀ value of 1.7 µM, breast cancer resistant protein (BCRP) (IC₅₀=0.23 µM) and OATP1B1 (IC₅₀=1.25 µM). Thus, its concomitant use with P-gp, BCRP or OATP1B1 substrates could lead to clinical drug-drug

interactions. Midostaurin drug transport inhibition experiments indicated that midostaurin is not likely to be a substrate of P-gp, multi-drug resistance associated protein 2 (MRP2), and is not actively taken up into the liver.

Preclinical toxicology

Midostaurin has been extensively evaluated in various *in vitro* systems and *in vivo* models. Studies relevant to clinical dosing of midostaurin include repeat dose toxicology studies with durations of up to 52 weeks, genetic toxicology, reproductive and developmental toxicity, juvenile toxicity and safety pharmacology studies. Additional toxicology studies have been performed with the combination of midostaurin and daunorubicin/cytarabine. No carcinogenicity studies have been performed.

Overall, the effects of treatment with midostaurin observed in the toxicology studies have been essentially limited to those expected from an inhibitor of cell proliferation. The no observable effect level (NOEL) in the 12-month toxicity studies was 3 mg/kg in rat and 1 mg/kg in dog. In-vitro and in-vivo mutagenicity tests revealed no genotoxicity. There was no teratogenic effect noted from embryo-fetal development studies in rats and rabbits. Developmental toxicity was seen at 10 mg/kg or higher. NOEL for fertility and general reproductive toxicity was defined at 30 mg/kg.

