15. Women of child-bearing potential, defined as all women physiologically capable of becoming pregnant, unless they are using highly effective methods of contraception during dosing and for at least 4 months after stopping medication. Highly effective contraception methods include:
 - Total abstinence (when this is in line with the preferred and usual lifestyle of the subject). Periodic abstinence (e.g., calendar, ovulation, symptothermal, post-ovulation methods) and withdrawal are not acceptable methods of contraception
 - Female sterilization (have had surgical bilateral oophorectomy with or without hysterectomy), total hysterectomy, or tubal ligation at least six weeks before taking study treatment. In case of oophorectomy alone, only when the reproductive status of the woman has been confirmed by follow up hormone level assessment
 - Male sterilization (at least 6 months prior to screening). The vasectomized male partner should be the sole partner for that subject
 - Use of oral, injected or implanted hormonal methods of contraception or placement of an intrauterine device (IUD) or intrauterine system (IUS), or other forms of hormonal contraception that have comparable efficacy (failure rate <1%), for example hormone vaginal ring or transdermal hormone contraception.
 - Midostaurin may reduce the effectiveness of hormonal contraceptives; therefore, females using systemically active hormonal contraceptives should add a barrier method of contraception.

Women are considered post-menopausal and not of child bearing potential if they have had 12 months of natural (spontaneous) amenorrhea with an appropriate clinical profile (i.e., age appropriate, history of vasomotor symptoms) or have had surgical bilateral

oophorectomy (with or without hysterectomy), total hysterectomy, or tubal ligation at least six weeks ago. In the case of oophorectomy alone, only when the reproductive status of the woman has been confirmed by follow up hormone level assessment is she considered not of child bearing potential.

16. Sexually active males unless they use a condom during intercourse while taking the drug during treatment, and for at least 4 months after stopping treatment and should not father a child in this period. A condom is required to be used also by vasectomized men as well as during intercourse with a male partner in order to prevent delivery of the drug via semen.
17. Unwillingness or inability to comply with the protocol.

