7.2.2.5.5 Pregnancy and assessments of fertility

Women of child-bearing potential will have serum pregnancy tests at screening. During the treatment phases, the absence of pregnancy will be confirmed by urine pregnancy test prior to the first dose of study treatment (at day 1 during induction, prior to each consolidation cycle and Day 1 during post-consolidation cycles).

Urine pregnancy tests will be required to be performed as well as at the End of Treatment visit and at 30-day Safety follow up visit. Every effort must be made for the women of child bearing potential to return to the site for the final pregnancy test. However if the patient is unable to return then the patient will administer the urine pregnancy test at home using the kit provided. For all pregnancy test performed at home, the site personnel will follow up with the patient via telephone call to collect the date and the test results and document the information in the patient's source documents.

Women of child-bearing potential will be instructed to contact the site immediately at any time during the study (on treatment or during follow-up) should they have a positive pregnancy test.

Male patients treated with idarubicin, daunorubicin or cytarabine should receive appropriate advice on the risk of infertility and the option of sperm conservation. Midostaurin may impair both male and female fertility and this should be communicated to the patients.

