10.5.3 Safety objectives

10.5.3.1 Analysis set and grouping for the analyses

For all safety analyses, the safety set will be used. All listings and tables will be presented by treatment group.

The overall observation period will be divided into three mutually exclusive segments:

1. Pre-treatment period: from day of patient's informed consent to the day before first dose of study treatment
2. On-treatment period: from day of first dose of study medication to 30 days after last dose of study medication
3. Post-treatment period: starting at day 31 after last dose of study medication.

The safety summary tables will include only assessments collected within 30 days after study treatment discontinuation and assessments prior to the data cut-off date for ongoing patients, unless otherwise specified.

All data, regardless of observation period, will be listed and assessments collected in the pretreatment and post-treatment period will be flagged in all the listings.

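### The 24-hour duty to report a pregnancy to the sponsor (protocol section 8.4) ends with study treatment, earlier than the protocol's own contraception period of at least 4 months

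*Protocol*

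**What the plan says.** Section 8.4 opens with the only pregnancy-reporting duty that carries a deadline: "each pregnancy occurring while the patient is on study treatment must be reported to Novartis within 24 hours of learning of its occurrence". It names no period after treatment.

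Two other parts of the protocol look past the last dose. Exclusion criterion 15 bars women of child-bearing potential "unless they are using highly effective methods of contraception during dosing and for at least 4 months after stopping medication". Criterion 16 requires men to use a condom during treatment and "for at least 4 months after stopping treatment and should not father a child in this period". Under section 7.2.2.5.5, women are to be "instructed to contact the site immediately at any time during the study (on treatment or during follow-up) should they have a positive pregnancy test". The same section sets the last scheduled tests: "Urine pregnancy tests will be required to be performed as well as at the End of Treatment visit and at 30-day Safety follow up visit".

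For partners, section 8.4 is broader: "Pregnancy outcomes should be collected for the female partners of any males who took study treatment in this study". That sentence has no time limit. The follow-up schedule in 8.4, which runs to 12 months after the expected delivery date for live births, covers both female patients and female partners.

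**The concern.** The protocol sets a period after the last dose in which conception is to be avoided, and it asks women to report a positive test to the site during follow-up. The step from site to sponsor is where the text stops. A site that learns of a pregnancy conceived two months after the last dose, and then reads section 8.4, finds a trigger limited to pregnancies on study treatment.

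At stake is the completeness of pregnancy-outcome data. Section 1.2.1.1 states that "Developmental toxicity was seen at 10 mg/kg or higher". It also states that rat and rabbit embryo-fetal studies showed no teratogenic effect, and section 11.3 has women told that risks to the fetus may be unknown. When a risk is uncertain, outcomes are best collected for every exposed pregnancy, normal births included. A route that depends on the investigator suspecting causality will not do that.

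**Working it through.** There is no sample size, power or error rate to reproduce here. The check compares passages and counts days.

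**1. When on study treatment ends.** Section 8.4 does not define the phrase. There are two candidate readings:
- *Last dose.* The glossary places study treatment discontinuation at the moment the patient permanently stops taking it. This is the plain reading.
- *Last dose plus 30 days.* Section 10.5.3.1 gives "On-treatment period: from day of first dose of study medication to 30 days after last dose of study medication", and SAP section 3.6.2 agrees. These definitions sort data for safety summaries, and 8.4 does not refer to them.

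**2. Days not covered for a female patient.** Contraception period: 4 months × 30 days = 120 days (4 × 30.4375 = 121.75 with average months). The protocol says at least 4 months, so this is a minimum.

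| Reading | Days with the 24-hour duty | Days without it |
|---|---|---|
| Ends at last dose | 0 of 120 | 120 |
| Ends 30 days later | 30 of 120 | 120 − 30 = 90, or 90/120 = 75% |

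Average months give 121.75 and 121.75 − 30 = 91.75 days, again about 75%.

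**3. What other routes pick up.**
- *Testing:* the last scheduled test is at the 30-day visit. The survival calls in section 7.1.8 ask about survival status and new antineoplastic medication, not pregnancy.
- *Serious adverse events:* section 8.2.1 counts a congenital anomaly as serious. Section 8.2.2 requires all serious events to be reported until at least 30 days after treatment, and after that only those with suspected causality. An uncomplicated pregnancy with a normal birth meets neither test.
- *Timing of conception:* the trigger in 8.4 is when the pregnancy occurs, not when it is found. A pregnancy conceived on treatment and discovered later is covered. The gap concerns conceptions after treatment.

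**4. Exposure after the last dose (context only).** Section 1.2.1.2 gives median terminal half-lives of 20.5 h for midostaurin, 32.3 h for CGP62221 and 471 h for CGP52421. Assuming simple first-order decay, the fraction remaining is 0.5^(hours / half-life).
- CGP52421 at day 30: 0.5^(720/471) = 34.7%. At day 120: 0.5^(2880/471) = 1.4%.
- Five half-lives: midostaurin 5 × 20.5/24 = 4.3 days; CGP62221 5 × 32.3/24 = 6.7 days; CGP52421 5 × 471/24 = 98 days.

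One active metabolite therefore persists beyond either reading of on treatment. The parent drug and the other metabolite are largely gone within a week.

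**The case against.** The strongest reply is that only the opening sentence of 8.4 carries the on-treatment limit. The next paragraph has pregnancies recorded on a dedicated form and reported to the sponsor's safety department without repeating that limit. Later text speaks of a pregnancy in a patient in the study, of tracking all prospective cases received, and of reporting any serious event during pregnancy. A careful site could read all this as an open-ended duty. That has force: the defect is an unclear trigger, not a total absence of reporting text. But the form paragraph follows directly on a sentence that sets the scope, and a site could equally read it as limited in the same way. A reporting rule should not depend on which reading a site chooses.

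A reader might go further and infer that every pregnancy in the 4 months goes unreported. The documents do not support that. Women are tested at end of treatment and at day 30, they are told to notify the site during follow-up, and a birth defect remains reportable after day 30 if causality is suspected.

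A reader might also extend the gap to partners. Outcome collection for partners has no end date, so it is not cut off at the last dose.

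Finally, the 35% figure might be taken as a measure of fetal risk. It is not. It describes the longest-lived analyte only. SAP section 9.6.1 weights that analyte at 0.06, against 1.40 for CGP62221, and those weights concern activity in AML. The protocol calls the 4 months a contraception period and does not quantify fetal risk within it.

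**Conclusion.** The concern holds in a limited form. For female patients, the explicit 24-hour duty is shorter than the contraception period in section 5.3 and is not tied to the notification instruction in section 7.2.2.5.5. About 90 to 120 days lack a clear duty to report and follow up, depending on whether the 30-day analysis definition is read into 8.4. The 120-day figure rests on the plain reading that treatment ends at the last dose. Both figures take 4 months as the minimum period.

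The number of pregnancies affected cannot be estimated from the documents. The finding concerns safety reporting only; EFS, OS, error rates, power and sample size are untouched. SAP section 1 records that the study stopped for futility but that some patients chose to continue study treatment, so the period could still apply to them.

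**What to change.** Reconcile section 8.4 with sections 5.3 and 7.2.2.5.5. In the opening sentence of 8.4, extend the trigger for female patients so that reporting and outcome follow-up apply to any pregnancy that occurs on study treatment or before the end of the post-treatment contraception period in exclusion criterion 15. Referring to the criterion, rather than restating a number of months, keeps the two in step. In 7.2.2.5.5, add a cross-reference so that a positive test notified during follow-up is passed on under 8.4.

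Leave the partner sentence in 8.4 unchanged. Adding a 4-month limit there would narrow a provision that is now open-ended.

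The cost is one amended sentence and a cross-reference, with the approvals that section 12.1 requires for any amendment. There may be a few extra reports, each with follow-up to 12 months after the expected delivery date for a live birth. No visit or test is added, and no dose or treatment rule changes.
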